2 STUDY OBJECTIVES

Specific Aims: In the U.S., 12% of livebirths are PTD and 8-10% are LBW, resulting in more than **\$26 billion** in medical costs *annually*¹⁰. The impact on infant health and the staggering costs makes PTD one of the top research priorities of **PCORI, AHRQ**¹¹, the Institute of Medicine (**IOM**) and the World Health Organization (**WHO**)⁸⁻¹⁰.

Genital herpes infection is prevalent, with a recent WHO estimation of 500 million people worldwide infected⁴⁴. Treating pregnant women with genital herpes infection, especially before the 3rd trimester, has been shown to reduce the risk of PTD and LBW^{21,35}, thus it can be an effective intervention to reduce PTD/LBW. However, the effectiveness and benefit of treating genital herpes to reduce PTD and LBW needs to be further demonstrated in order to be incorporated into the development of treatment guidelines and clinical practice. Currently, many pregnant women choose *not to treat* genital herpes due to a general aversion to taking medications during pregnancy for the safety of their fetuses, and a lack of evidence of benefits. Paradoxically, the choice of no treatment for genital herpes may adversely impact fetal health, leading to PTD and LBW^{17-22,35}. Given that pregnant women frequently prefer no treatment, studies are urgently needed to establish the risk-benefit profile between treatment and no treatment for genital herpes infection in the context of improving fetal health, including the timing of treatment (before the 3rd trimester). This study is designed to provide clear evidence of treatment effectiveness in real-world clinical practice, and risk-benefit profiles to inform both treatment decisions by pregnant women and clinicians, and evidence-based policy recommendations by CDC and the U.S. Preventive Services Task Force. ***This proposed comparative effectiveness study will address the following questions:***

1. Does treating genital herpes infection in pregnant women reduce the risk of adverse pregnancy outcomes including PTD or LBW? (treated vs. untreated)
 2. Does the *timing* of the treatment during pregnancy influence the treatment effectiveness on reducing adverse pregnancy outcomes (PTD and LBW)? (head-to-head comparison of treatment timing: before the 3rd trimester vs. during the 3rd trimester).
 3. Do other treatment metrics, including treatment duration, dosage, and compliance, impact treatment effectiveness in reducing the risk of PTD and LBW?

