Point and interval estimates of the relative hazards of PTD associated with first treatment during pregnancy before and first treatment during the 3rd trimester will be obtained (Cohort A vs. B) by extending the Aim 1 regression model to capture treatment timing. Parameter estimation, the approach to inclusion of potential confounders, modeling of continuous covariates, and model diagnostics are as described above for Aim 1 analyses. Treatment will be handled as a time-varying covariate for proper classification of exposure status in each risk set for the Cox regression (three levels: no treatment, first treatment < 3rd trimester, treatment in 3rd trimester). Significance of the difference between strength of association across the two treatment timing categories will be assessed via a Wald test.

Aim 3. Do other treatment metrics, including treatment duration, dosage, and compliance, impact treatment effectiveness in reducing PTD and LBW risk?

Metrics of treatment exposure of interest will be treated as time-dependent covariates in Cox regression analyses to account for changes in exposure status during follow-up, including cumulative duration (categorized as no use, 1-5 days, 6-10 days, 11-30 days, and > 30 days) based on clinical prescription patterns, and cumulative dose (categorized as no use, 1-4,800mg, 4,801-12,000mg, and >12,000 mg) also based on current clinical prescription patterns. In addition to examining these metrics in relation to pregnancy outcomes during the entire pregnancy, we will also assess trimester-specific measures of treatment duration and dose.

Aim 4. Does treatment effectiveness vary depending on the type (or severity) of underlying genital herpes infection? (e.g. treating symptomatic genital herpes infection vs. treating latent/asymptomatic genital herpes)

Analyses will examine potential heterogeneity in association between treatment and PTD across infection characteristics via the inclusion of appropriate cross-product terms and a likelihood ratio test, and point and interval estimates of association at each level of the effect modifier will be obtained via appropriate transformed linear combinations of regression parameter estimates.

Aim 5. Does genital herpes infection in pregnancy, if untreated, increase the risk of PTD and LBW, compared to no genital herpes infection? (untreated vs. controls without genital herpes) .

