Power calculations are based on the likelihood ratio test in the context of a Cox proportional hazards regression analysis for PTD, and a logistic regression analysis for LBW, as presented by Self⁵⁸ and as implemented in the software package EGRET⁵⁹. Given previous experience⁶⁰⁻⁶³, we expect negligible loss to follow-up (< 0.20%), a rate of PTD ranging from 8% - 12%⁶⁴, and LBW ranging from 8% to 10%⁶⁵. Each primary contrast of interest in analyses addressing **Aims 1, 2 and 5** can be characterized as a comparison of two groups of women with respect to risk of PTD and LBW. Minimum (maximum, for protective effects) detectable associations are of modest to moderate strength (Table 6). The proposed study will have more than sufficient power to detect the associations observed in our preliminary studies. Relevant to **Aim 3**, we present the maximum (protective effects assumed) detectable pattern of hazard ratios (HR) across cumulative treatment duration categories (no treatment, 1 – 10 days (45% among treated), > 10 days (55% among treated)). For the purpose of detectable effect calculations, we assume a graded, linear trend in (log) hazard/odds ratios across duration categories, a two-sided test for trend and a significance level of .05. We have sufficient power (.80) to detect a pattern of PTD HRs of 1.0 (ref), .82, and .67 associated with no treatment, 1-10 days and >10 days, respectively, assuming the worst case

scenario of expected 8% PTD rate. Similarly, we have sufficient power (.80) to detect a pattern of

Table 6. Minimum (maximum for protective scenarios) detectable hazard ratios (HR) for preterm delivery and detectable odds ratios (OR) for low birthweight in pair-wise comparisons of genital herpes exposure/treatment categories; two-sided test, significance level (α) = .05, power (1- β) =.80.

Contrast	Preterm Delivery (HR)		Low Birthweight (OR)	
	Rate = 8%	Rate = 11%	Rate = 8%	Rate = 10%
Treated infection vs. untreated infection (Aim 1; A+ B vs. C)	.71	.75	.70	.72
Treated < 3 rd trimester vs. 3 rd trimester (Aim 2, A vs. B)	.66	.71	.65	.68
Untreated infection vs. no infection (Aim 5, C vs. D)	1.51	1.40	1.54	1.47

odds ratios ORs of 1.0 (ref), .81, and .66 associated with no treatment, 1-10 days and >10 days, respectively, assuming the worst case scenario of expected 8% LBW rate.

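### Aim 3 asks about dosage as distinct from duration, but dose is defined only as cumulative milligrams and no planned model separates it from days of treatment

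*Combined protocol and SAP*

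**What the plan says.** Section 2, question 3, sets the aim: "Do other treatment metrics, including treatment duration, dosage, and compliance, impact treatment effectiveness in reducing the risk of PTD and LBW". Section 4.2 repeats it for the analysis, again naming duration, dosage and compliance side by side.

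Section 4.2 then defines two measures, both time-dependent in the Cox model for preterm delivery (PTD). Duration is "cumulative duration (categorized as no use, 1-5 days, 6-10 days, 11-30 days, and > 30 days) based on clinical prescription patterns". Dose is "cumulative dose (categorized as no use, 1-4,800mg, 4,801-12,000mg, and >12,000 mg) also based on current clinical prescription patterns". It adds that "we will also assess trimester-specific measures of treatment duration and dose". Low birthweight (LBW) is handled in parallel by logistic regression.

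Section 4.5 gives detectable effects for duration only, using a "two-sided test for trend and a significance level of .05". It splits treated women into 1-10 days (45%) and "> 10 days (55% among treated"). It gives no detectable effect for dose. Section 3.1 speaks of anti-herpes medications as a class, with acyclovir as an example. The documents state neither a daily dose nor a distribution of total dose.

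**The concern.** Dosage is a separate question from duration only if it can be examined at a given duration. Total milligrams cannot do that alone: a woman reaches a higher dose class by taking more per day, by being treated longer, or both. If only duration mattered, the dose classes would usually still show a trend, because longer treatment moves women up the dose scale. Conversely, if higher daily amounts went with shorter courses, a real dosage effect could be hidden.

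Nothing else in the plan separates the two. The trimester measures are the same totals over shorter periods. The propensity score in Section 4.3 models treatment against no treatment, so it does not balance duration across dose classes. No cross-classification or mutual adjustment is described, and no rule says how milligrams of different drugs are combined. At stake is a dosage statement, in a study meant to inform treatment guidance, that may be a duration finding under another name.

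**Working it through.** **1. Reproducing the plan's own Aim 3 figure.** Inputs from Section 4.5: effective sample 1,200 per cohort, so 1,200 untreated and 2,400 treated; PTD rate 8%; two-sided 0.05; power 0.80; treated women split 45%/55%.
- Events = 3,600 × 0.08 = 288.
- Scores 0, 1, 2 with shares 0.333, 0.300, 0.367: mean 1.033, variance 1.767 − 1.068 = 0.699.
- (1.960 + 0.842)² = 7.849. Slope = √(7.849 / (288 × 0.699)) = 0.197.
- Hazard ratios: exp(−0.197) = 0.82 and exp(−0.395) = 0.67, as stated.

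The duration calculation is therefore sound. There is no counterpart for dose to check.

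**2. What a pure duration effect looks like on the dose scale.** Identity: cumulative mg = average daily mg × days. Take the Section 4.5 pattern (0.82 for 1-10 days, 0.67 for more than 10) and assume no dosage effect.
- The top class (>12,000 mg) needs more than 12,000/d days at daily amount d. For d ≤ 1,200 mg this is at least 10 days (12,000/1,200 = 10), so everyone in it has more than 10 days: hazard ratio 0.67.
- The bottom class (up to 4,800 mg) allows at most 4,800/d days. For d ≥ 480 mg this is at most 10 days (4,800/480 = 10), so everyone in it has 1-10 days: hazard ratio 0.82.
- The middle class mixes the two and lies between.

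So for any mix of daily amounts within 480-1,200 mg (an assumed range), the dose analysis shows 0.82 falling to 0.67 with no dosage effect present. Outside that range the classes mix: at 400 mg/day the bottom class extends to 12 days, and at 3,000 mg/day the top class begins above 4 days.

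**3. How strongly the two sets of classes overlap.** Simulation under these assumptions: lognormal durations with 55% above 10 days, log-SD 0.6 to 1.2, days rounded, daily dose independent of duration and in equal shares. Spearman correlation between duration class and dose class:

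| Assumed daily amounts (mg) | Correlation |
|---|---|
| 1,200 only | 0.92-0.96 |
| 800 / 1,200 | 0.82-0.90 |
| 400 / 800 / 1,200 | 0.70-0.86 |
| 400 / 1,200 / 3,000 | 0.48-0.71 |

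The overlap weakens as daily dose spreads but remains material even in the widest mix.

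**4. What a daily-dose term could detect.** Assume a 50/50 high/low split and 8% PTD. Detectable HR = exp(−√(4 × 7.849 / events)).
- Effective sample, all treated: 2,400 × 0.08 = 192 events, HR 0.67.
- Effective sample, more than 10 days: 192 × 0.55 = 105.6 events, HR 0.58.
- All Stage I treated women (2,100 + 2,100 = 4,200): 336 events, HR 0.74; more than 10 days, 184.8 events, HR 0.66.

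These are best cases. An unequal split, or correlation between daily dose and duration, makes them weaker.

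**The case against.** The best defence is that cumulative dose is a legitimate total-exposure measure, that Aim 3 introduces its metrics with wording that leaves the list open, and that trimester-specific dose is also planned. The cut-points are attributed to prescribing patterns that a reader cannot see, and the plan nowhere says a dose trend will be taken as independent of duration. A daily-dose term would also have limited power. All of this is fair, and it is why cumulative dose should stay. But an open list pre-specifies nothing, and trimester totals carry the same product of amount and time.

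Three stronger readings are tempting and are not supported:
- That dose merely repeats duration. This holds only if daily dose is nearly constant, which the documents do not say; with a wide mix the class correlation falls to 0.48-0.71.
- That about half of treated women fall in the top dose class. The 55% in Section 4.5 concerns more than 10 days and carries over to more than 12,000 mg only at an assumed 1,200 mg/day. Under the lognormal durations above, before rounding to whole days, the share is 4-22% at 400 mg/day and 71-84% at 2,000 mg/day.
- That the open-ended top class hides sustained treatment from the study. The duration scale already separates 11-30 days from more than 30. Without a dose distribution, splitting the top dose class is a matter of preference.

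**Conclusion.** As specified, Aim 3's dosage question cannot be answered separately from its duration question. That follows from the definitions and needs no assumption. The size does need one: the spurious gradient is the full 0.82 to 0.67 when daily amounts lie within 480-1,200 mg, and is diluted when they spread more widely, provided daily dose is unrelated to duration. If the two are related, it could be larger, smaller or reversed. The documents do not say which case applies.

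The point is confined to the dosage part of Aim 3. It should be settled before analysis, because a dosage metric chosen after seeing results would be post hoc.

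**What to change.** In Section 4.2, Aim 3:

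1. Define average daily dose as dispensed milligrams divided by days' supply, calculated within drug, so that milligrams of different drugs are not pooled.
2. Estimate its effect among treated women in a model that also contains cumulative duration. For PTD make both time-dependent, counting a woman's person-time from first treatment; for LBW use the logistic counterpart. Restricting to treated women also avoids the shared no-use reference, which would make the two categorical terms collinear.
3. Base the Aim 3 dosage conclusion on the daily-dose term. Keep cumulative dose as a descriptive measure of total exposure, and say so.
4. Report the joint distribution of daily dose and duration, and give a detectable effect for the daily-dose term in Section 4.5.

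The cost is SAP wording and one variable from the prescription and dispensing data of Section 3.3.3, which must already yield milligrams and days for the planned metrics. The downside is wider intervals for the daily-dose term, especially if regimens vary little; in that case the plan should report that dosage could not be assessed. These are analysis variables only and imply no recommended dose.

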Treating pregnant women is unique in that it impacts *both* the mother and her developing fetus. CDC has highlighted a new initiative called "**Treating for Two**" and advocated research into medication use during pregnancy to take into account the effectiveness and risk-benefit profiles for both pregnant women and the developing fetus (<http://www.cdc.gov/pregnancy/meds/treatingfortwo/>)⁴². Currently, symptomatic genital herpes infection in pregnancy, usually considered more severe than asymptomatic genital herpes, is mostly treated with anti-herpes medications, such as acyclovir, that are effective in suppressing viral shedding and symptoms²³. Acyclovir is also recommended for treating genital herpes after 36 weeks of gestation to prevent vertical transmission of maternal herpes infection to the newborn^{23,24}. On the other hand, asymptomatic genital herpes before 36 weeks of gestation is often left untreated because of a lack of recognized benefits for fetal outcomes (e.g., reducing PTD and LBW). Thus, many women with mild or asymptomatic genital herpes are left untreated, and, consequently, at increased risk of PTD and LBW^{17,19-22}. Untreated genital herpes infection was associated with more than twice the risk of PTD and more than 40% of increased risk of LBW, compared to controls as described above. More importantly, if treated with acyclovir, women with genital herpes had a more than 50% reduced risk of PTD (OR=**0.49**, 95%CI=0.36-0.68), and 40% reduced risk of LBW (OR=**0.60**, 95%CI=0.37-0.98) than women who were not treated (Tables 2). Our preliminary results showed that the currently recommended treatment of herpes infection with acyclovir, if expanded to treat pregnant women with genital herpes before the 3rd trimester, could largely mitigate the risk of PTD and LBW associated with genital herpes infection. This treatment effectiveness was also consistent across subtypes of PTDs.

A lack of consistency in treating genital herpes infection in pregnant women is largely due to the knowledge gap regarding (1) increased risk of PTD and LBW associated with untreated

genital herpes infection in pregnant women, and (2) evidence of treatment effectiveness in reducing PTD and LBW, in addition to preventing mother-newborn vertical transmission of herpes infection^{17,19-21,35}.

A.4. Existing knowledge gaps

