risk factors that may be plausibly linked to infection and PTD. Inclusion or exclusion of potential confounding factors in our final regression models will be evaluated based on comparison of the regression coefficient associated with the contrast of interest (treated vs. untreated) both adjusted and unadjusted for the potential confounder under consideration (i.e. inclusion if regression coefficient changes by 10% or more). The change-in-estimate approach to confounder selection performs well with regard to power, bias, mean squared error and confidence interval coverage for the primary factor of interest⁴⁵. Continuous potential confounders will first be categorized either as quartiles, or into clinically relevant categories (e.g. BMI classification, amount of cigarette smoked or alcohol intake). The shape of the association/pattern of regression coefficients across increasing levels of the categorized covariate, of interest in their own right, will serve as a guide in the approach to modeling the variable as a continuous independent variable. A simple linear term may be appropriate, but higher order polynomial terms may be necessary to capture any non-linearity in association. Departures from model assumptions will be assessed via diagnostic plots of weighted residuals and tests for interaction between exposure and time (gestational age).

Analyses of LBW as the outcome will parallel those described above for PTD, but logistic regression techniques will be used rather than Cox regression, in Aims 1 – 5.

Aim 2. Does the timing of the treatment during pregnancy influence the treatment effectiveness on reducing adverse pregnancy outcomes (PTD and LBW)? (A head-to-head comparison of treatment timing: before the 3rd trimester vs. during the 3rd trimester).

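### For low birthweight in Aim 3, whole-pregnancy and 3rd-trimester treatment totals stop at delivery, so early birth itself lowers measured exposure and biases the dose-response toward benefit

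*Combined protocol and SAP*

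**What the plan says.** Section 4.2, Aim 3: "Metrics of treatment exposure of interest will be treated as time-dependent covariates in Cox regression analyses to account for changes in exposure status during follow-up". Duration is "categorized as no use, 1-5 days, 6-10 days, 11-30 days, and > 30 days" and dose is "categorized as no use, 1-4,800mg, 4,801-12,000mg, and >12,000 mg". The plan adds that, besides "examining these metrics in relation to pregnancy outcomes during the entire pregnancy, we will also assess trimester-specific measures of treatment duration and dose".

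The model for LBW is set at the end of the Aim 1 text in section 4.2. LBW analyses parallel those for PTD, except that "logistic regression techniques will be used rather than Cox regression, in Aims 1 – 5".

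Section 4.3 (propensity score) applies conditional logistic regression to LBW for each exposure metric, stratified on deciles of a score for treatment versus no treatment. If its results differ from the conventional ones, it supplies the main findings.

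Section A.3 of the background gives the practice context: "Acyclovir is also recommended for treating genital herpes after 36 weeks of gestation to prevent vertical transmission". Section 3.3.3 expects 2,100 women in Cohort A, 2,100 in Cohort B (first treated in the 3rd trimester) and 6,600 in Cohort C.

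**The concern.** Time-dependent exposure protects the PTD analysis because, at each gestational age, women are compared on what they have accumulated so far. A logistic model for LBW has one exposure value per woman. If that value is the pregnancy total, its window closes at delivery.

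Take three women with the same plan, daily treatment from 36 weeks:

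- Delivery at 39 weeks: 7 × (39 − 36) = 21 days, in the 11-30 day group.
- Delivery at 37 weeks: 7 × (37 − 36) = 7 days, in the 6-10 day group.
- Delivery at 35 weeks: 0 days, counted as no use.

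The >30 day group is reached only after 36 + 30/7 = 40.3 weeks. Risk of LBW falls with gestational age, so the categories sort women partly by outcome risk. A 3rd-trimester total has the same defect, since delivery sets the length of that window.

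Aim 3 asks whether more treatment works better. A dose-response produced by the length of pregnancy could be read as support for longer treatment.

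**Working it through.** **1. The plan's own figure.** Section 4.5 gives, at 80% power, 8% LBW and a two-sided .05 trend test, detectable LBW odds ratios (ORs) of 1.0, .81 and .66 for no treatment, 1-10 days and >10 days. Inputs: effective size 1,200 per cohort, with 45% and 55% of treated women in the two duration groups. Sizes are therefore 1,200, 0.45 × 2,400 = 1,080 and 0.55 × 2,400 = 1,320.

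Model: logit π_j = a + b·s_j, with s = 0, 1, 2. Noncentrality: λ = 2 Σ n_j [π_j ln(π_j/π̄) + (1 − π_j) ln((1 − π_j)/(1 − π̄))]. Power = P(χ²₁(λ) > 3.841).

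With π̄ = 0.08 and b = ln(.66)/2, the risks are 0.096, 0.080 and 0.066, λ = 7.96 and power = 0.806. Solving for power .80 gives ORs of 0.814 and 0.662. The plan's figure reproduces, and .66 is >10 days versus **no treatment**.

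**2. Simulation of a drug with no effect** (1,500,000 pregnancies per scenario). Treatment plans are independent of outcome and treatment stops at delivery.

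- Gestational age (assumed): preterm births at 37 minus an exponential with mean 2.5 weeks; term births at 37 plus a gamma (shape 4.5, scale 0.5), capped at 42 weeks. PTD is 8% or 11%, within section 4.5's range.
- Birthweight (assumed): 3,380 + 175 × min(GA − 39.5, 1) g, SD 470 g. LBW is <2,500 g. This gives 8.2% LBW at 8% PTD; the plan states 8-10%.
- Treatment in the scenario closest to the protocol (assumed): 21% have a 7- or 14-day course before 28 weeks, 18% take daily treatment from about 36 weeks, and 6% have a 7-day course in the 3rd trimester.

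Check against section 3.3.3: planned treatment reaches 1 − 0.79 × 0.82 × 0.94 = 39.1% of infected women, against 4,200/10,800 = 38.9%. The share of these first treated in the 3rd trimester is 0.79 × (1 − 0.82 × 0.94)/0.391 = 46%, against 50%. The realised split at 10 days is 46/54, against 45/55.

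LBW odds ratios on whole-pregnancy days, versus no treatment:

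| Assumed pattern | 1-10 days | >10 days | Trend OR per step | Trend test rejects, n = 3,600 / 10,800 |
|---|---|---|---|---|
| 18% daily from 36 weeks, PTD 8% | 1.00 | 0.60 | 0.81 | 74% / 99% |
| Same, PTD 11% | 0.96 | 0.53 | 0.76 | 96% / 100% |
| 6% daily from 36 weeks | 0.95 | 0.80 | 0.90 | 15% / 48% |
| 18% daily from 32 weeks | 1.00 | 0.81 | 0.91 | 23% / 55% |
| Almost all short courses before 28 weeks | 0.95 | 0.97 | 1.00 | 6% / 5% |

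The nominal rejection rate is 5%. The sizes are 3 × 1,200 and 2,100 + 2,100 + 6,600. In the first row, LBW is 8.9%, 8.9% and 5.6% across the three groups. Over the plan's five duration categories the ORs are 1.0, 2.13, 0.98, 0.71 and 0.23.

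A second simulation (8% PTD, 10% LBW, about half of treated women first treated in the 3rd trimester) gave about 0.45 for >10 days with daily treatment from 36 weeks and about 0.73 from 32 weeks. With up to two 7-day courses spread over weeks 4-40 and no continuous use, the ORs were 0.85-0.88 and 0.74-0.75.

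**3. Third-trimester days only.** In the four scenarios with daily late treatment, the null OR for >10 days is 0.42-0.77.

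**4. Exposure closed at a fixed week, among women undelivered then.** Counting to 28 weeks, the null ORs are 0.99-1.02 (1-10 days) and 1.00-1.01 (>10 days). Counting to 36 weeks, they are 0.97-1.02 and 0.96-1.04. The artefact disappears.

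Dose was not simulated separately; at a constant daily dose, milligrams follow days.

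**The case against.** **The size is not known.** This stands. The documents do not say what share of women continue treatment to delivery. A reader might infer that a useless drug is bound to show a strong dose-response. The table does not support that: results run from null to substantial. The null row, however, has almost no treatment starting in the 3rd trimester, which does not fit 2,100 women in Cohort B.

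**The comparison with .66 must be like for like.** A reader might set a >10 versus 1-10 day odds ratio against .66. That is the wrong yardstick: the plan's implied value for that contrast is .66/.81 = 0.81. Contrasts against 1-10 days also look larger because early deliverers collect in that reference group. Only ORs versus no treatment are compared with .66 here.

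**The effect inside Cohort A.** A reader might conclude that it must persist there. It does so only if Cohort A women continue or restart treatment late. The 36-week recommendation makes this plausible, but no figure is given.

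**The plan already holds part of the answer.** True. The 1st- and 2nd-trimester measures are nearly free of the artefact, and PTD is handled properly by the time-dependent Cox model.

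**The text is silent rather than wrong.** Parallel analysis might be read as carrying the protection over. But the protection comes from the Cox risk set, which the LBW sentence removes, and the stated window is the entire pregnancy. Tables 4 and 5 are not in the text available; if either fixes an exposure window, the point narrows accordingly.

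**Propensity scores, or LBW independent of PTD.** The score balances determinants of treatment; delivery date is not one of the pre-treatment covariates. The preliminary LBW result independent of PTD (section A.2) is not carried into the plan. In a simulation restricted to term births, the >10-day odds ratio returned to 1.0, but >30 versus 1-10 days stayed at 0.32.

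**Conclusion.** The concern holds in conditional form. As written, the LBW logistic models for Aim 3, including the propensity-score version, use whole-pregnancy and 3rd-trimester totals that end at delivery. The direction of bias is toward apparent benefit.

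On the plan's own contrast, the null odds ratio for >10 days is about 0.45-0.60 if many treated women take daily treatment from 36 weeks. That is at or beyond the .66 the study is powered to detect. It is about 0.73-0.81 if daily treatment starts at 32 weeks or late use is limited, and the trend is about null if almost all treatment is short courses before 28 weeks. These figures rest on assumed prescribing patterns and an assumed relation of birthweight to gestational age. The mechanism and direction rest on the text.

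The point does not extend to the PTD Cox analyses, nor materially to the 1st- and 2nd-trimester measures.

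**What to change.** In the LBW models for Aim 3, conventional and propensity-score, replace whole-pregnancy and whole-3rd-trimester totals with duration and dose accumulated to fixed gestational weeks, among women still undelivered at that week:

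- the end of the 2nd trimester (taken as 28 weeks above; the SAP should state the week) for early exposure;
- prespecified later landmarks, for example 32 and 36 weeks, or an equivalent time-updated exposure model, for 3rd-trimester exposure.

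Keep the planned 1st- and 2nd-trimester measures and the time-dependent Cox metrics for PTD. Do not rely on adjusting for week of delivery. It brought the null odds ratios close to 1 (0.94-1.04, apart from one sparse cell at 0.88), but it conditions on a possible mediator and so changes the question.

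Cost: SAP wording and reprogramming, with data already held. Each landmark model omits earlier births and ignores later treatment. The end-of-2nd-trimester landmark counts every Cohort B woman, half of those treated (2,100 of 4,200), as not yet treated. It therefore cannot stand alone for late treatment, and the later landmarks are needed alongside it.
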